5.5. Early Patient Termination/Patient Withdrawal

Patients who discontinue treatment early due to PD, a DLT, or withdrawal will be asked to have all EOT safety evaluations performed as described in the protocol (see the Schedule of Assessments [[Table 1](#), [Table 2](#), and [Table 3](#)]). If a patient withdraws from treatment during Cycle 1 due to any reason other than a DLT and does not meet the minimum requirements for inclusion in the DLT-evaluable population described in Section [4.3.3](#), an additional patient may be enrolled to ensure an adequate number of evaluable patients.

5.6. Pharmacokinetic Assessments

The plasma PK parameters (including $AUC_{0-\infty}$, $AUC_{(0-\tau)}$, C_{max} , T_{max} , $t_{1/2}$, Cl/F , and Vd/F) of BDTX-189 following oral administration will be assessed by analysis of blood plasma samples (see [Table 10](#)). Patients participating in the Dose Escalation cohorts during Part A will undergo detailed PK evaluation according to [Table 10](#). Patients participating in the initial Dose Escalation where BDTX-189 was evaluated fasting should also take the study drug fasting for the detailed PK assessment. Patients enrolled in cohorts evaluating BDTX-189 in the non-fasting state should be provided a meal of their choice in connection with the detailed PK assessment as instructed in Section [6.1.2](#).

All patients enrolling into the Safety Expansion will have blood drawn on Day 1 of Cycles 2, 3, 4, 5 and every other cycle thereafter for sparse pop PK sampling. In addition, a minimum of 12 patients in the Safety Expansion will be administered a smaller and reformulated 200 mg tablet and will undergo detailed PK evaluation according to [Table 10](#) on C1D1 and C1D15. This evaluation will be performed at selected study sites capable of performing detailed PK

procedures. Detailed PK sampling will be collected on Day 15 (i.e., after 14 days of daily treatment with the smaller and reformulated 200 mg tablet) of that subsequent cycle according to [Table 10](#).

Table 10 BDTX-189 pharmacokinetic collection times (Part A Dose Escalation and Safety Expansion patients)

Study Day	PK draws (hours post-dose) ^a	Collection window (\pm mins)
C1D1	pre-dose ^c	
	0.5	5
	0.75	5
	1 ^c	10
	1.5	10
	2 ^c	15
	3 ^c	15
	4 ^c	20
	6	30
	8 ^d	30
	24 ^e	30
C1D15^b	pre-dose ^c	
	0.5	5
	0.75	5
	1 ^c	10
	1.5	10
	2 ^c	15
	3 ^c	15
	4 ^c	20
	6	30
	8 ^d	30
	24 ^e	30
Sparse PK Sampling (Pop PK)		
Cycles 2, 3, 4, 5 and every other cycle thereafter (\pm 2 days)	Pre-dose 1 st sample: 0.5 - 1.5 hours post-dose ^a 2 nd sample: 2 - 4 hours post-dose ^a	n/a

Abbreviations: C = Cycle; D = Day; mins = minutes; n/a = not applicable; PK = pharmacokinetic.

a The actual post-dose time of collection should be recorded.

b Patients in Part A who initiated treatment with the larger 200 mg tablet may be switched to the smaller and reformulated 200 mg tablet at the beginning of their subsequent cycles. Detailed PK sampling will be collected on Day 15 (i.e., after 14 days of daily treatment with the smaller 200 mg tablet) of that subsequent cycle.

c ECG measurements will be performed in triplicate pre-dose and at 1.0, 2.0, 3.0, and 4.0 hours (+/- 5 minutes) post-dose on C1D1 and C1D15 starting with dose level 4 (200 mg) and onwards for the QD schedule and starting with dose level 1 for the BID dosing schedule. For each set of triplicate ECGs, 3 standard resting 12-lead ECGs will be obtained in close succession and not more than 2 minutes apart (4 minutes total for 3 ECGs); see Section [5.3.2](#).

d Patients on the BID schedule should have their 8-hour PK samples drawn prior to the second dose of the day.

e The 24-hour sample will be collected prior to the administration of study drug on Day 2 or Day 16, as appropriate.

In Part A, time-matched ECG measurements will be collected coinciding with the detailed PK assessments around the projected C_{max} in patients to evaluate any QTc concentration-effect relationship. See [Table 1](#), [Table 2](#), and Section [5.3.2](#) for specific time points.

For Part B, sparse PK blood samples will be collected at approximately the following time points:

- Cycles 1 to 5 and every other cycle thereafter (± 2 days), Day 1: One pre-dose, two post-dose blood draws, the 1st draw at 0.5 – 1.5 hours post-dose and the 2nd draw at 2 – 4 hours post-dose.

Note: An ad hoc PK sample should be drawn (whenever possible) in case of a severe adverse event or at pre-dose in the event of dose modification, to assess the safety of the patient.

5.6.1. Pharmacokinetic Assessments – Food Effect (Part A)

Plasma PK parameters (including AUC_{0-INF} , $AUC_{(0-\tau)}$, C_{max} , T_{max} , $t_{1/2}$, Cl/F , and Vd/F) of BDTX-189 following oral administration in a fed/fasted state will be assessed by analysis of blood samples at the time points specified in [Table 11](#).

Table 11

BDTX-189 pharmacokinetic collection times – Lead-in phase for Food-Effect (Part A)

Study Day	PK draws (hours post-dose)	Collection window (\pm mins)
Day -4	pre-dose	
	0.5	5
	0.75	5
	1	10
	1.5	10
	2	15
	3	15
	4	20
	6	30
	8	30
Day -1	pre-dose	
	0.5	5
	0.75	5
	1	10
	1.5	10
	2	15
	3	15
	4	20
	6	30
	8	30

Abbreviations: mins = minutes; PK = pharmacokinetic.

Note: Beginning with Cycle 1 Day 15, PK sampling will continue as per all other patient cohorts (see Table 10). There is no PK sampling on C1D1 for patients in the Food-Effect cohort.

5.7. Biomarker Assessments

5.7.1. Archival Tumor Samples

Tumor samples will be collected during the screening period for retrospective confirmation of allosteric *ErbB* mutations using a diagnostic test that is being developed. Archival tumor samples or tumor tissue from a new pretreatment biopsy is required for all patients enrolled in the Safety Expansion portion of Part A and Part B who have allosteric *ErbB* mutations. Archival tumor samples or tissue from a new pretreatment biopsy is requested for patients with allosteric *ErbB* mutations enrolled in the Dose Escalation portion of Part A.

Samples should be provided as a tissue block. Alternatively, if a tissue block cannot be provided 12-20 freshly cut formalin-fixed paraffin-embedded (FFPE) unstained slides may be submitted. Freshly cut unstained slides are preferred, however unstained slides that were sectioned within 2 years prior to the patient enrolling in the study may be submitted only if stored in the appropriate long-term storage conditions (-80°C). If the quantity of archival tumor tissue available is insufficient to obtain 12-20 unstained slides, a new tumor tissue biopsy sample must be obtained prior to starting study treatment.

Further details on sample processing, handling, and shipment are provided in the Laboratory Manual.

5.7.2. Fresh Biopsies

Patients in the Dose Escalation portion of Part A will be required to undergo baseline and on-treatment tumor biopsies if the tumor is amenable for biopsy in the opinion of the Investigator. For patients participating in the Safety Expansion cohort(s) or any cohort in Part B an archival tumor tissue sample is required, if an archival tumor tissue sample is not available, a fresh tumor biopsy will be required at baseline.

In Part A, the on-treatment biopsy is planned to be obtained from dose level 5 (400 mg) or an earlier dose cohort (e.g., 200 mg) if emerging data suggest and continue at higher dose levels until data supports target engagement in downstream signaling. Fresh tumor biopsies will be collected at baseline (or within 28 days of baseline) and on C2D1 (± 5 days). On C2D1, patients must be dosed in the clinic at least 2 hours prior to collecting the biopsy. The biopsy may be collected up to 8 hours after dosing. Depending on emerging PDx data, the C2D1 biopsy may be collected pre-dose in either the BID cohorts or both cohorts. Pre-dose biopsies may be collected 12 hours after a BID dose or 24 hours after a QD dose. This sample will be used to investigate changes in pathway signaling and potential mechanisms of resistance (e.g., ERK phosphorylation, evidence of alternative pathway activation [e.g., PI3K/AKT], and co-occurring genomic alterations). The material must include both FFPE and fresh frozen tissue. A minimum of 2 and ideally 4 core biopsies should be obtained. Detailed sample processing, handling, and shipment are provided in the Laboratory Manual.

All patients in Part A and Part B will be asked to undergo an optional on-treatment tumor biopsy at the time of disease progression if the tumor is amenable for biopsy in the opinion of the Investigator and the patient consents.

Evaluable paired on-treatment samples will be used to evaluate exploratory biomarkers. Failure to obtain a sufficient tumor sample after making best efforts to biopsy the tumor will not be considered a protocol deviation. When feasible, collection of an optional tumor biopsy at relapse is encouraged but will not be considered to be a protocol deviation if the patient does not give or withdraws consent.

Biopsies should be obtained through non-significant risk procedures. Sampling should be undertaken by experienced physicians in appropriate settings. The on-treatment biopsy can be omitted if clinically contraindicated or if the risk of the procedure for the individual patient has increased to a significant level as determined by the Investigator.

Instructions regarding sample collection, sample handling/processing, and sample shipping are provided in the Laboratory Manual. This will include instruction regarding study drug administration to be done in the clinic at least 2 hours prior to obtaining the tumor biopsy.

5.7.3. Blood Samples for Circulating Tumor DNA (ctDNA)Analysis

Blood samples will be collected for exploratory analysis of ctDNA mutations to assess correlations with disease activity, effects of study drug, and clinical outcomes. Blood samples will be collected from all patients to generate plasma samples and these samples will be used for the extraction and analysis of ctDNA. The samples will be used to explore the relationship between changes in biomarkers and response to treatment. In addition, innate and acquired resistance mechanisms may be explored. Markers tested may include, but will not be limited to, allosteric *ErbB* mutations, resistance mutations (e.g., [REDACTED]), and alterations in other genes involved in [REDACTED] and [REDACTED] signaling. Similarly, the relationship between other blood-borne biomarkers and drug response and/or PD may be explored. During treatment, ctDNA blood samples will be taken at the following time points:

Part A Dose Escalation (includes Food-Effect Cohort patients)

- Cycle 1 Day 1: pre-dose.
- Cycle 2 Day 1: pre-dose.
- Cycle 3 Day 1: pre-dose.
- End of study treatment/PD.

Part A Safety Expansion Cohort(s)

- Cycle 1 Day 1: pre-dose.
- Cycle 2 Day 1: pre-dose.
- Cycle 3 Day 1: pre-dose.
- Cycle 5 Day 1: pre-dose.
- End of study treatment/PD (If not collected at the EOT visit, these samples may be collected at the 30-Day Safety Follow-up visit as long as no new anticancer therapy has commenced).

Part B

- Screening
- Cycle 1 Day 1: pre-dose.
- Cycle 2 Day 1: pre-dose.
- Cycle 3 Day 1: pre-dose.
- Cycle 5 Day 1: pre-dose.
- Cycle 7 Day 1: pre-dose.
- Cycle 9 Day 1: pre-dose.
- One pre-dose sample will be collected every 4th cycle (Cycle 13 Day 1, Cycle 17 Day 1, Cycle 21 Day 1, etc.).
- End of study treatment/PD (If not collected at the EOT visit, these samples may be collected at the 30-Day Safety Follow-up visit as long as no new anticancer therapy has commenced).

Instructions regarding sample collection, handling/processing, and shipping are provided in the Laboratory Manual.

6. DRUG FORMULATION, AVAILABILITY, ADMINISTRATION, AND RISK INFORMATION

6.1. BDTX-189

Investigational Product	Dosage Form and Strength	Manufacturer
BDTX-189	100 mg and 200 mg tablets (A smaller and reformulated 200 mg tablet may be administered to some patients in select sites during the Safety Expansion of Part A and to all patients enrolling onto Part B).	Black Diamond Therapeutics, Inc.

6.1.1. Labeling, Packaging, and Supply

The Sponsor will supply the BDTX-189 as tablet formulations of 100 and 200 mg. A smaller and reformulated 200 mg tablet may be introduced during the Safety Expansion of Part A to select sites, and will also be administered to patients enrolling onto Part B. Each high density polyethylene (HDPE) bottle will contain 30 tablets. This tablet is a common granulated blend of drug substance and pharmacopeial grade excipients compressed into an immediate release form, which is half the size of the larger 200 mg tablet provided to patients in the Dose Escalation portion of Part A. The pharmacopeial grade excipients include starch, microcrystalline cellulose, croscarmellose sodium, sodium dodecyl sulfate, colloidal silicon dioxide, and magnesium stearate.

Patients in Part A who initiated treatment with the larger 200 mg tablet may be switched to the smaller and reformulated 200 mg tablet at the beginning of their subsequent cycles after instruction by the Sponsor.

At each visit, patients will be dispensed sufficient supplies until the next visit. Study drug compliance will be assessed at each patient visit by review of the dosing diary. The research staff will count and document the amount of study drug taken and returned by the patient. The batch number of the study drug dispensed to the patient should be entered on the eCRF, if applicable.

The immediate packaging will contain a statement to conform with FDA Investigational New Drug (IND) requirements as follows: "Caution: New Drug - Limited by federal (or United States) law to investigational use." and according to the applicable local laws for labeling the investigational products

All study drugs must be kept in a secure place under appropriate storage conditions. Storage conditions for BDTX-189 are included on the investigational product label.

The Sponsor or its representative must be granted access on reasonable request to check drug storage, dispensing procedures, and accountability records.

6.1.2. Preparation and Administration of BDTX-189

BDTX-189 is administered PO. The study drug will be provided to the sites by the Sponsor.

The emerging food-effect data suggest a slight to moderate increase in systemic exposure of BDTX-189 when administered with a high fat meal. Therefore, separate cohorts (QD and BID)

at ≥ 800 mg/day will be evaluated in the fed state, as will the Safety Expansion cohort(s) and Part B. In this case, patients will be instructed not to take study drug on an empty stomach. Patients are allowed to take their dose of BDTX-189 with approximately 240 mL water within 30 minutes of completing a meal.

Tablets should be swallowed whole (along with up to 240 mL water), not crushed, chewed, or dissolved.

For the QD dosing schedule, patients will self-administer the study drug with approximately 240 mL water within 30 minutes of completing a meal. The time of day for administration of BDTX-189 should be as consistent as possible.

For the BID dosing schedule, BDTX-189 should be taken at approximately the same time each morning and approximately the same time each evening, approximately 10 hours after the morning dose. Patients will self-administer the study drug with approximately 240 mL water within 30 minutes of completing a meal.

For the Food-Effect Patients, study drug will be self-administered on an empty stomach following a fast of approximately 2 hours. Patients will continue to fast for approximately 1 hour after the administration of BDTX-189.

On scheduled PK collection days, C1D1 and C1D15 during Dose Escalation and Safety Expansion, the patient should be instructed to wait until he/she arrives at the study center and receives instructions from the research staff to take their morning dose of study medication.

On the scheduled on-treatment tumor biopsy day, the patient in Part A should be instructed to wait until he/she arrives at the study center and receives instructions from the research staff to take their study medication. Study drug administration will take place at least 2 hours prior to obtaining the tumor biopsy.

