
Study Drugs, Doses, and Modes of Administration:
	
BDTX-189 will be supplied as 100 mg and 200 mg tablets. Treatment cycles will be 21 days. A smaller and reformulated 200 mg tablet may be administered to some patients enrolling at select sites during the Safety Expansion cohort(s) of Part A, and to all patients enrolling onto Part B. Prior to exceeding the MTD for the QD schedule, patients received BDTX-189 in a fasted state. With the implementation of Amendment 3 all patients enrolling in Part A and Part B must take BDTX-189 immediately after or with a standard meal. Patients in Part A who initiated treatment with the larger 200 mg tablet may be switched to the smaller and reformulated 200 mg tablet at the beginning of their subsequent cycles at the discretion of the Sponsor.
 
During the Dose Escalation portion of Part A the starting dose was 25 mg BDTX-189 PO QD; an alternative dosing schedule (BID) was implemented based on the analysis of emerging PK and safety/tolerability. After the 400 mg QD dose regimen was declared tolerable by the Safety Review Committee (SRC) a separate cohort of patients was assessed for food effect in a randomized, single-dose crossover fashion in the fed/fasted state (see Section 4.3).
 
For Part B, BDTX-189 will be administered PO at the RP2D (800 mg, daily total).

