^o Urinalysis will include protein, glucose, ketones, urobilinogen, occult blood, and microscopic sediment evaluation. A 24-hour urine collection for assessment of urine protein will be performed whenever the urinalysis reveals \geq 3+ protein.

^p Negative serum β -hCG pregnancy test within 7 days prior to the first dose of study drug will be required as an entry criterion for WOCBP. For WOCBP, a urine sample or serum pregnancy test will be performed on Day 1 of Cycle 2-Cycle 5, then at each subsequent in-person visit while patient is on treatment (including the EOT visit).

^q See Section 5.6 and Table 10 for full PK profile and sparse PK sampling schemes. On PK collection days, patients should be instructed to wait until they arrive at the study center and receive instructions from study staff prior to taking their dose of study medication. Sparse PK will also be collected (sampling scheme: C2D1, C3D1, C4D1, C5D1 and every other cycle thereafter [\pm 2 days], 1 pre-dose sample and 2 post-dose blood draws: the 1st draw at 0.5-1.5 hours post-dose and the 2nd draw at 2-4 hours post-dose.) Refer to Table 10. Patients participating in the initial Dose Escalation where BDTX-189 was evaluated fasting should also take the study drug fasting for the detailed PK assessment. Patients receiving BDTX-189 in the non-fasting state should be provided a meal of their choice in connection with the detailed PK assessment as instructed in Section 6.1.2.

^r ctDNA samples will be obtained pre-dose on C1D1, C2D1, C3D1, and at the EOT visit and/or time of disease progression for all patients enrolling onto Part A, including Food-Effect patients. If not collected at the EOT visit, these samples may be collected at the 30-day Safety Follow-up visit as long as no new anticancer therapy has commenced. (See Section 5.7.3)

^s After dose level 5 (400 mg QD) has been deemed tolerable by the SRC, or a later cohort has been deemed tolerable based on emerging data, Food Effect will be assessed during a lead-in phase for patients in that cohort. On Day -4, patients will be randomized to receive BDTX-189 as a single oral dose after fasting for at least 10 hours before dosing or immediately after consuming breakfast. Patients receiving the study drug in the fasted state will continue to fast for at least 4 hours after the dose. Patients will receive BDTX-189 in the opposite prandial state on Day-1 (see Section [5.3.1](#)).

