4.3. Treatment Plan

BDTX-189

BDTX-189 will be provided as tablets for oral administration in dose strengths of 100 and 200 mg. Additionally, a smaller and reformulated 200 mg tablet will be administered to some patients at select sites enrolling in the Safety Expansion of Part A and all patients enrolling onto Part B.

Prior to exceeding the MTD for the QD schedule, patients received BDTX-189 in a fasted state. As of January 2021, based on the recommendation of the SRC (details provided in Section 1.1.7), all patients will receive BDTX-189 with approximately 240 mL water within 30 minutes of completing a meal (Section 6.1.2). The time of day for BDTX-189 administration should be consistent. For patients receiving BDTX-189 BID, the 2 doses should be separated by at least 10 hours.

Patients enrolling into the Food Effect cohort will be dosed in the fed/faasted state as per [Table 1](#) and Section 5.3. On scheduled PK collection days (Cycle 1 Day 1 and Cycle 1 Day 15 for Part A, and Days -4 and -1 for the Food Effect Cohort), patients will be instructed to wait until they arrive at the study center to take their study drug when told.

In Part B, patients will be administered BDTX-189 at the RP2D identified during Part A (800 mg QD, non-fasting).

If the patient misses a dose of study drug, the patient should take the dose as soon as possible but not less than 12 hours before the next dose is due for QD dosing. If the next dose is due in less than 12 hours, the patient should skip the missed dose and take the next dose as scheduled. If the patient in a BID cohort misses a dose of study drug, the patient should take the dose as soon as possible but not less than 6 hours before the next dose is due for BID dosing. If the next dose is due in less than 6 hours, the patient should skip the missed dose and take the next dose as scheduled.

If vomiting occurs more than 30 minutes after taking the study treatment, the patient should be instructed not to retake that dose. Patients should take the next scheduled dose of BDTX-189. If vomiting persists, the patient should contact the Investigator.

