Patients will receive BDTX-189 as a single oral dose on Day -4 after fasting for at least 10 hours before dosing or immediately after consuming a high-fat breakfast. Patients will receive BDTX-189 in the opposite prandial state on Day -1. BDTX-189 will be administered QD in 21-day cycles starting on C1D1. On the assigned day of PK assessment in the fed state, 30 minutes prior to the planned BDTX-189 administration time, patients will be instructed to consume a high-fat meal (see below for an example breakfast) and must finish the meal within 30 minutes. Patients will be instructed to take their dose of BDTX-189 with approximately 240 mL water within 30 minutes after starting the high-fat meal. On the assigned day of PK assessment in the fasted state, BDTX-189 will be administered together with approximately 240 mL water, following an overnight fast of at least 10 hours. Patients should not consume any food for at least 4 hours after the dose. The use of agents that suppress gastric acidity (H2 receptor antagonists, proton pump inhibitors, and intraluminal antacids) and agents that delay gastric emptying are prohibited from 1 week prior to the Day -4 dose until C1D1, when only proton pump inhibitors will be prohibited, as described in Section 4.5.2. Please see Table 11 (PK Sample Collection Food Effect Part A) for specific time points.

Patients will be given a high-fat breakfast in order to assess food effects on the PK of BDTX-189. An example high-fat breakfast that will be provided is a standard McDonald's

breakfast, which might include an Egg McMuffin, bacon, hash browns, and milk. Note: Alternative food components/quantity and/or time (i.e., lunch) may be allowed as per timing of dose administration and as approved by the Investigator/Sponsor. In addition, a low-fat breakfast may also be assessed as emerging data dictate. An example low-fat breakfast may include 8 ounces of milk (1% fat), one boiled egg, and one packet flavored instant oatmeal with water (approximately 400-500 calories).

5.3.2. *Electrocardiogram Measurements*

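### Section 6.1.2 gives Food-Effect patients an empty-stomach rule with no study day attached; it conflicts with the lead-in crossover conditions or, for later enrollees, with the fed-dosing rule

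*Combined protocol and SAP*

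**What the plan says.** Three sets of instructions bear on how Food-Effect patients take the drug.

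- **Section 6.1.2.** "For the Food-Effect Patients, study drug will be self-administered on an empty stomach following a fast of approximately 2 hours". The next sentence adds: "Patients will continue to fast for approximately 1 hour after the administration of BDTX-189". Neither is limited to a study day or period. The same section has patients on the once-daily schedule dose after a meal, and places cohorts at 800 mg/day and above, the Safety Expansion and Part B in the fed state.
- **Section 5.3.1 and Table 1 footnote s.** For the fasted lead-in dose, Section 5.3.1 specifies dosing "following an overnight fast of at least 10 hours. Patients should not consume any food for at least 4 hours after the dose". Footnote s agrees, describing a "single oral dose after fasting for at least 10 hours before dosing or immediately after consuming breakfast". Each patient takes the other lead-in dose in the opposite condition. Daily dosing then starts on Cycle 1 Day 1, with no prandial condition given in Section 5.3.1.
- **Section 4.3 and the Synopsis.** Section 4.3 states that, as of January 2021, "all patients will receive BDTX-189 with approximately 240 mL water within 30 minutes of completing a meal". Its next paragraph sends the Food Effect cohort to Table 1 and Section 5.3. The Synopsis says that, once Amendment 3 is implemented, "all patients enrolling in Part A and Part B must take BDTX-189 immediately after or with a standard meal"; that sentence makes no exception for Food-Effect patients.

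**The concern.** A site that looks up administration in Section 6.1.2 finds one instruction addressed to Food-Effect patients, and cannot tell whether it covers the lead-in doses, the daily dosing that follows, or both.

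Two things depend on the answer. The first is the crossover. The fed/fasted geometric least squares mean ratio with its 90% CI is the endpoint for a secondary objective (Table 4), and Section 9.5.6 compares that interval with 80–125%. If the fasted dose followed a much shorter fast, and some food effect remained, the AUC ratio would be pulled towards 1.

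The second is daily dosing. Section 4.3.2.1 keeps these patients out of the DLT-evaluable population but has their safety information considered in dose decisions and in determining the RP2D. Under Section 5.3.1 they may continue at 800 mg QD, and Section 1.1.7 reports tolerability by prandial state. Food-Effect patients kept fasted at a nominal dose that others take fed would not be like for like.

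**Working it through.** The plan states no figure to reproduce, and no sample-size or power calculation applies. The check sets the passages side by side and does simple arithmetic on the stated times and counts.

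**1. The fasts compared**

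| | Section 6.1.2 | Section 5.3.1 and footnote s | Difference |
|---|---|---|---|
| Before dose | about 2 h | at least 10 h | 10 − 2 = 8 h or more |
| After dose | about 1 h | at least 4 h | 4 − 1 = 3 h or more |
| Fed dose | none provided for | one of the two lead-in doses | – |

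Section 1.1.7 gives a fasted median t_max of 1.5 h. Under Section 6.1.2 food is allowed at about 1 h, before that median; under Section 5.3.1 it is withheld until at least 4 h, after it.

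**2. If Section 6.1.2 governs Days -4 and -1.** It contradicts the 10 h/4 h condition. Read literally it also removes the fed period, because it puts every dose on an empty stomach.

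**3. If Section 6.1.2 governs dosing from Cycle 1 Day 1.** It no longer touches Section 5.3.1, which is silent from that day. For patients enrolled after the switch, it contradicts the Synopsis sentence, the general rule in Section 4.3 and the once-daily paragraph of Section 6.1.2. For patients enrolled before the switch it can stand. The switch itself is dated in two ways: January 2021 in Section 4.3 and Amendment 3 (08 June 2021) in the Synopsis.

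**4. The Cycle 1 Day 15 PK day.** The note to Table 11 has Food-Effect patients rejoin the common PK schedule on that day. Table 1 footnote t makes its prandial condition depend on whether the patient is being dosed fasting or non-fasting, which is what step 3 leaves open for this cohort.

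**5. Who could still be affected.** Section 5.3.1 plans up to 8 patients per meal type, 2 × 8 = 16. Section 1.1.7 reports 6 evaluable per meal type at 02 April 2021, 2 × 6 = 12, with the cohorts ongoing. That leaves 16 − 12 = up to 4 PK-evaluable patients, plus any added if a pivotal food-effect study is wanted, which Section 5.3.1 allows.

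**6. Size of bias.** Section 1.1.7 gives a high-fat-meal AUC ratio of 2.3. Suppose, purely as an assumption, that a fraction f of that effect persists after a 2 h fast. The apparent ratio is then 2.3/(1 + 1.3f):

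- f = 0: 2.3
- f = 0.25: 2.3/1.325 = 1.74
- f = 0.5: 2.3/1.65 = 1.39
- f = 1: 2.3/2.3 = 1.0

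The documents give no information on f, so the range covers everything from no bias to complete loss of the effect.

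**The case against.** The strongest reply is that the day-specific instructions are consistent. Section 5.3.1 and footnote s agree, Section 4.3 refers this cohort to them, and lead-in patients wait at the study center to be told when to dose. A site following those passages would run the crossover consistently. The Section 6.1.2 sentence describes self-administration with no fed option, so it reads more naturally as a home-dosing rule, perhaps left over from the earlier fasted regimen. The fed rule is also bounded in time: Section 1.1.7 applies the Safety Review Committee's recommendation to patients still to be enrolled, and 12 of up to 16 food-effect patients were already evaluable by April 2021. These patients are outside the BOIN decision rules, their PK is analysed separately, and 800 mg QD non-fasting is already the stated MTD and RP2D.

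Most of this stands and limits the point. It does not remove it: Section 6.1.2 neither says that it is a home-dosing rule nor names the patients it covers, the cohort was still open, and the Synopsis makes no exception.

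Three stronger readings are tempting and are not supported:

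- **The general fed rule contradicts the lead-in fast.** Within Section 4.3 it does not, because the next paragraph exempts this cohort.
- **The fasted PK data are wrong, with a true ratio of 2.3 reported as roughly 1.4 to 1.7.** Those values come only from choosing f between 0.25 and 0.5. The documents contain neither the choice nor evidence that any patient fasted for 2 h.
- **Food-Effect patients dosed fasted at home differ about 2.3-fold in exposure from fed patients.** The 2.3 is AUC after a high-fat meal; the C_max ratio in the same sentence is 1.0, and routine fed dosing uses a standard meal or a meal of choice.

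**Conclusion.** The contradiction is real and lies in current operative text. Its extent depends on the days to which Section 6.1.2 applies: on the lead-in days it conflicts with both crossover conditions; from Cycle 1 Day 1 it conflicts with the fed-dosing rule, but only for Food-Effect patients enrolled after the switch. A daily-dosing reading fits those enrolled earlier.

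The stated fasts differ by about 8 h or more before the dose and 3 h or more after it. On planned numbers, up to 4 further PK-evaluable patients were exposed to the ambiguity at the April 2021 cut-off, more if the cohort is enlarged; this assumes that the cohort was still recruiting under the current text, as Section 1.1.7 implies. The effect on the fed/fasted ratio cannot be sized. This is an inconsistency within the protocol that should be corrected, not evidence that results are compromised.

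**What to change.** Reconcile Section 6.1.2 with Section 5.3.1, Table 1 footnotes s and t, Section 4.3 and the Synopsis. State separately:

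- the prandial conditions on Days -4 and -1;
- the prandial condition from Cycle 1 Day 1 onward, including the Cycle 1 Day 15 PK day;
- the enrolment period to which each applies, with one date or event for the switch to fed dosing.

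Which fasting rule should prevail is for the sponsor and investigators to settle; no view is taken here.

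Record the actual prandial state on each PK day and flag departures from the reconciled condition. Their handling in the fed/fasted ratio belongs in the separate PK analysis plan that Section 9.5.6 mentions. Automatic exclusion should not be assumed: it presupposes which rule governs, and dropping one period breaks a patient's pairing in a crossover of 12 to 16 patients.

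The cost is a wording change in a protocol amendment, one flag in the data and a short entry in the PK analysis plan.
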